## **Rationale of dose/regimen, duration of treatment**

The immunosuppressant drugs, basiliximab, tacrolimus, mycophenolate mofetil, corticosteroids (methylprednisolone/prednisone), and everolimus are marketed drugs and their dosage and administration will be based on label recommendations and clinical standards of care

## **Study Population**

The study population will consist of adult (age >18 years) male and female primary liver transplant recipients. All patients will have received a liver allograft from a deceased donor.

It is anticipated our center will need to screen approximately 140 male and female adult liver transplant recipients. Of these 140 liver allograft recipients, it is expected a minimum of 90 will fulfill the inclusion and none of the exclusion criteria at baseline and will be able to be randomized in a 2:2:1 manner to receive one of the three proposed immunosuppressive regimens.

## **Inclusion Criteria at Baseline**

Patients eligible for inclusion in this study have to fulfill all of the following criteria:

1. A signed informed consent prior to patient participation in the study and before any assessment is performed.
2. Patients who are able to take oral medication at 1 month post transplant

3.  $\geq 18$  years old
4. Undergoing first OLT
5. Dialysis for 45 days or less at time of transplant
6. Able and willing to conform to requirements of the study
7. Able and willing to provide informed consent or have legally authorized representative who is able and willing to provide informed consent

## **Exclusion Criteria**

1.  $< 18$  years old
2. Autoimmune liver disease, Primary Sclerosing Cholangitis, Primary Biliary Cirrhosis
3. Dialysis greater than 45 days
4. Receiving ATG, IVIG therapy, or sirolimus/everolimus around time of transplant or sirolimus/everolimus after transplant
5. Unable to take oral medications at 1 month post transplant
6. Participating in another clinical research study involving the evaluation of another investigational drug or device
7. Documented allergy to basiliximab, TAC, MMF or any macrolide antibiotic.
8. Presence of thrombosis of any major hepatic arteries
9. Complex/high risk arterial reconstruction at any time (graft vessel patency by Doppler ultrasound confirmed and documented).
10. Patients who are recipients of multiple solid organ transplants, (e.g., multivisceral or combined liver-kidney transplants), or have previously received an organ or tissue transplanted, or who received an ABO incompatible transplant.
11. Patients who have severe hypercholesterolemia ( $>215$  mg/dL;  $>5.5$  mmol/L) or hypertriglyceridemia ( $>265$  mg/dL;  $>3.0$  mmol/L) at Baseline.
12. Patients who have severe thrombocytopenia or neutropenia (platelet count  $>20$  and MLCs $>1000$ )
13. Patients who have any surgical or medical condition, which in the opinion of the investigator, might significantly alter the absorption, distribution, metabolism and excretion of study drugs
14. Patients with a known hypersensitivity to the drugs used on study or their class, or to any of the excipients.
15. Patients with clinically significant systemic infection
16. Pregnant or nursing (lactating) female patients, where pregnancy is defined as the state of a female after conception and until the termination of gestation, confirmed by a positive  $\beta$ HCG laboratory test ( $>9$  mIU/mL) at Baseline.

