Similar to the CNIs, everolimus administration includes trough level therapeutic drug monitoring (TDM). This practice has evolved largely due to the relatively narrow therapeutic window for immunosuppression, the considerable inter- and intraindividual pharmacokinetic variability, as well as the high incidence of drug-drug interactions resulting from hepatic metabolism via cytochrome P450 isoenzyme 3A4 (CYP3A4). Results in adults using therapeutic drug level monitoring of everolimus target an everolimus C-0h blood trough level of 3-8 ng/mL. [27, 28]

Previously, the risk of hepatic artery thrombosis (HAT), leading to an increased rate of patient death within the first 30 days post-transplantation, was identified as a concern after liver transplantation using sirolimus. [29] However, recent results suggest that sirolimus used at low doses or early after the immediate peri-operative period was not associated with HAT. [30] HAT has neither been associated with the use of everolimus. [31] However, the Phase III trial conducted in *de novo* adult whole liver transplantation implemented delayed everolimus administration (POD 30 ± 5 days) to limit the risk of drug induced HAT.

Therefore, based on the available data and experience in OLT recipients and building on our previous UCLA pilot trial design and experience, the potential benefit from the introduction of delayed everolimus and improved renal function related to reduction of calcineurin inhibitors (CNI) over time and enhanced safety profile warrants additional investigation.

Thus, we propose a randomized, prospective investigator initiated study that will compare basiliximab induction, delayed TAC exposure plus MMF and a SOC corticosteroid taper (group 1; n=36), compared to basiliximab induction, delayed TAC exposure plus MMF and a SOC corticosteroid taper with a delayed everolimus facilitated CNI reduction at POD 30 and mycophenolate minimization to further enhance renal function (group 2; n=36) versus control (standard dose TAC plus MMF and standard of care corticosteroid taper; group 3; n=18).

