## **Investigational Treatment**

### **Introduction and maintenance of everolimus**

Everolimus will be introduced at the earliest 1 month after liver transplantation for all patients to minimize the potential risks of wound healing and vascular complications of the graft. At the start of the treatment period (Day 1), patients will receive the first dose of everolimus (1 mg twice daily in 12 hr intervals)

By Day 4, the everolimus dose will be adjusted to achieve targeted C-0h blood trough level between 3-8 ng/mL. All patients will continue to receive everolimus with CNI reduced dose for 6 months. Mycophenolate will be minimized as clinically indicated in subjects (group 2) receiving everolimus and tacrolimus.

The dose of everolimus must be taken twice-daily, 12 hours apart, in the morning and evening dose AFTER tacrolimus administration (everolimus or tacrolimus dose administrations should not be more than 10 minutes apart). The morning or evening everolimus dose should be taken consistently either with or without food as the patient prefers. To prevent alteration of study drug absorption, grapefruit or grapefruit juice are not allowed throughout the study.

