## DRUG THERAPY

### *Group 1*

#### Basiliximab

- Dose #1: 20mg IV within 2 hours of transplant
- Dose #2: 20mg IV Post-operative day #4

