##### *Group 3 (control):*

#### Tacrolimus (without basiliximab induction)

- Beginning day #1 post-transplant to six months: 0.03-0.1mg/kg q12h PO to maintain whole blood trough concentration of 5-12ng/mL
- Six months to one year: maintain whole blood trough concentration of 5-10ng/mL

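### Exclusion 9, and exclusion 8 if it means graft thrombosis, has no cut-off at randomisation, so randomised patients could be dropped for a post-transplant vascular event

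*Protocol*

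**What the plan says.** Two items in the protocol's Exclusion Criteria concern the hepatic artery. Item 8 is "Presence of thrombosis of any major hepatic arteries". It gives no time window and does not say whether the artery is native or graft. Item 9 is "Complex/high risk arterial reconstruction at any time (graft vessel patency by Doppler ultrasound confirmed and documented". It has an explicitly open window and refers to the graft.

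The Study Population section places the eligibility decision before allocation: patients are to meet "none of the exclusion criteria at baseline and will be able to be randomized in a 2:2:1 manner". Neither baseline nor randomisation is dated relative to surgery.

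Arm-specific treatment starts around the operation. In Groups 1 and 2 basiliximab is "Dose #1: 20mg IV within 2 hours of transplant", and in Group 3 tacrolimus is given "Beginning day #1 post-transplant to six months".

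Graft vascular complications are part of the design rationale. Everolimus is held back for about a month "to minimize the potential risks of wound healing and vascular complications of the graft", and the Introduction reports that the Phase III trial used "delayed everolimus administration (POD 30 ± 5 days) to limit the risk of drug induced HAT".

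**The concern.** An exclusion criterion should be decidable from what is known when the patient is randomised. Item 9 fails this test as worded, because a complex reconstruction weeks after transplant would still meet it. If such a patient were ruled ineligible and taken out, the removal would rest on something that happened after assignment, and the arms would no longer be the groups that randomisation formed.

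The event in question is not incidental. Hepatic artery problems can lead to graft loss, which is a secondary endpoint (with death) and part of the composite efficacy failure. They are also the kind of complication that the delayed start of everolimus is meant to limit. Dropping such patients could lower the counts of outcomes that the trial sets out to compare.

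**Working it through.** **Arm sizes.** The synopsis gives 90 subjects at 2:2:1, that is 36, 36 and 18. Check: 90 × 2/5 = 36 and 90 × 1/5 = 18. The stated sizes reproduce.

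**Timing, step by step.**
1. Eligibility is judged at baseline and randomisation follows (Study Population).
2. The first treatment that separates Groups 1 and 2 from Group 3 falls within 2 hours of transplant (basiliximab) or on day 1 (control tacrolimus). Groups 1 and 2 share a regimen until about day 30, but the protocol describes a single 2:2:1 randomisation, so assignment should be known by the first of these times.
3. Item 9 needs an implanted graft for its Doppler condition and has no end date. It therefore runs past the time in step 2 and conflicts with step 1.
4. Item 8 raises the same conflict only if it means thrombosis of the graft artery.

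**Would a patient actually be dropped?**
- Towards removal: the Everolimus subsection on dose adjustments says that patients who cannot take oral medication by 1 month are excluded from the study. This applies exclusion 5, from the same list, after treatment has begun. The discontinuation list also includes significant protocol violation.
- Against removal: hepatic artery thrombosis is not in the discontinuation list. Patients who discontinue are followed for the full 6 months (Criteria for Early Withdrawal), and all adverse events are to be evaluated (Safety objectives).
- Undecided: the protocol's Statistical analysis section is still to be determined. The SAP's single paragraph names tests but gives no analysis set, no intention-to-treat statement and no rule for patients found ineligible after randomisation.

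**Size per patient.** 1/36 = 2.8 percentage points; 1/18 = 5.6 percentage points.

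**How many patients.** The documents give no rate, so the rates p below are assumptions. Expected number = n × p; chance of at least one = 1 − (1 − p)^n.

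| Assumed rate | Expected, n = 36 | Expected, n = 18 | Expected, all 90 | At least one, n = 36 | At least one, n = 18 |
|---|---|---|---|---|---|
| 2% | 0.7 | 0.4 | 1.8 | 52% | 31% |
| 5% | 1.8 | 0.9 | 4.5 | 84% | 60% |
| 10% | 3.6 | 1.8 | 9.0 | 98% | 85% |

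These are upper limits on removals at each rate, because they suppose that every event is found after randomisation and leads to removal.

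**Effect on a reported rate.** Suppose 2 of 36 patients have an event. Kept in the arm, the rate is 2/36 = 5.6% (exact 95% interval 0.7% to 18.7%). With both removed it reads 0/34 = 0%.

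**The case against.** Four points on the other side have force.

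- **Item 8 differs from item 9.** The open window is only in item 9. Item 8 can be read as a thrombosis present at baseline, including in a native artery, and then it raises no timing problem. A reader might infer that both items can be known only after transplant; the text does not show this for item 8.
- **The order of surgery and randomisation is not fixed.** The protocol speaks of screening recipients ("our center will need to screen approximately 140 male and female adult liver transplant recipients"), which leans towards enrolment after surgery. Inclusion criterion 4 (undergoing a first transplant) and the pre-transplant work-up under Treatment Procedures lean the other way. A reconstruction done during the operation could be known before assignment. This stands for intraoperative findings, but an open window also covers later ones.
- **No passage removes anyone under items 8 or 9.** A reader might infer that the plan deletes these patients and hides their events. The follow-up and adverse-event provisions point the other way. What remains is a risk: the wording permits removal, another exclusion is already used that way, and no analysis rule prevents it.
- **The link to everolimus is limited.** The Introduction says that hepatic artery thrombosis has not been associated with everolimus; the risk it describes was identified with sirolimus. Events before about day 30 precede everolimus in any case. Everolimus-period events would be lost only if the open window were applied after that. The criteria apply to all three arms, so nothing supports a claim that Group 2 alone would be affected.

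It can also be said that the root gap is the missing analysis set. That is fair, but a rule on analysis sets would not remove the contradiction between item 9 and eligibility at baseline.

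**Conclusion.** The point holds in a limited form. As written, exclusion 9 reaches past randomisation and conflicts with eligibility being settled at baseline; exclusion 8 does so only if it refers to the graft. With no analysis set defined, and a precedent for excluding patients at 1 month, randomised patients could be dropped for a vascular event that bears on graft loss and safety.

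The stronger conclusion, that the plan removes such patients and conceals an everolimus harm, is not supported. The per-patient figures (2.8 and 5.6 points) rest only on the planned arm sizes. Any statement of how many patients are affected rests on an assumed event rate and on removal in practice. The wording should be corrected, but the documents do not show that the comparison has been compromised.

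**What to change.** - Date baseline and randomisation relative to surgery.
- Limit exclusions 8 and 9 to information available at randomisation, and say in item 8 whether the native or the graft artery is meant.
- State in the SAP that every randomised patient is analysed in the assigned arm, including any later found to meet an exclusion.
- Name hepatic artery thrombosis and later arterial reconstruction as safety outcomes, reported by arm.
- If the two items are meant as a check before everolimus starts, take them out of trial eligibility and reconcile them with the Study Population section, the section on introducing everolimus and the discontinuation list. The clinical rule itself is for the investigators to set.

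These are wording changes and need no extra patients or visits. The downside is that patients who have a vascular event and never start everolimus stay in Group 2 and slightly dilute its estimated effect.

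### Exclusion 12 contradicts itself as printed: it names low counts but gives high-count limits, without units and with an undefined cell type

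*Protocol*

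**What the plan says.** Item 12 of the protocol's Exclusion Criteria names its condition and follows it with limits in a parenthesis: "severe thrombocytopenia or neutropenia (platelet count $>20$ and MLCs $>1000". Neither number has a unit. MLCs is not expanded there and appears nowhere else in the protocol or SAP.

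Three neighbouring items show how the same list uses parentheses:

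- Item 11 excludes patients with "severe hypercholesterolemia ( $>215$ mg/dL; $>5.5$ mmol/L", with a similar pair of limits for triglycerides. The limit defines who is excluded, and it has units.
- Item 16 confirms pregnancy by a positive "HCG laboratory test ( $>9$ mIU/mL) at Baseline". Again the limit defines who is excluded, with units.
- Item 9 reads "Complex/high risk arterial reconstruction at any time (graft vessel patency by Doppler ultrasound confirmed and documented". Here the parenthesis seems to describe an acceptable state rather than the reason for exclusion.

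The Study Population section gives the list its force: patients to be randomized are those who "fulfill the inclusion and none of the exclusion criteria at baseline".

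**The concern.** Thrombocytopenia and neutropenia are low counts, so a limit defining them would be expected to point downwards. Both signs in item 12 point upwards. The connectives differ too: the words need one low count, while the limits as printed need both conditions.

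What is at stake is eligibility checking. Whoever screens a patient has to decide what the parenthesis means, which units apply and which cell is counted. A monitor or reader who has only the protocol cannot confirm that the decision was right, or that it was made the same way for every patient. The Everolimus part of the section on permitted dose adjustments treats falls in platelet and white blood counts as reasons to adjust the dose, so the criterion plausibly bears on safety, although the protocol gives no rationale for item 12.

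**Working it through.** There is no sample size, power or event figure to reproduce. The check compares the words with the limits and then looks for text that settles the difference.

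**Step 1: the two readings.** Let P be the platelet count and M the MLC count, both on the printed scale.

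- Reading A, as in items 11 and 16, where the limit defines the excluded patient: excluded if P > 20 and M > 1000.
- Reading B, where the parenthesis is the state required for entry: excluded if not (P > 20 and M > 1000), that is, if P ≤ 20 or M ≤ 1000.

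**Step 2: compare each with the words.** Assume for this step only that M is the neutrophil count and that low means at or below the printed limit. The values are illustrative.

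| P | M | By the words | Reading A | Reading B |
|---|---|---|---|---|
| 10 | 500 | excluded | not excluded | excluded |
| 10 | 3000 | excluded | not excluded | excluded |
| 100 | 500 | excluded | not excluded | excluded |
| 100 | 3000 | not excluded | excluded | not excluded |

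Reading B matches the words in every row, and it explains the signs and the *and* together. They are therefore one drafting question, not two errors. Reading A contradicts the words in every row. The readings are exact complements, so they classify every patient oppositely.

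**Step 3: does the protocol say which reading applies?** It does not. The other items that print laboratory limits (11 and 16) follow the pattern of reading A. Item 9 offers a possible precedent for reading B, but it has no laboratory limit. No sentence marks the parenthesis in item 12 as an entry requirement.

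**Step 4: does any other text repair the line?** The Inclusion Criteria at Baseline set no blood-count limit. The dose-adjustment text for everolimus mentions falling platelets and white cells without a number or unit. The SAP does not deal with eligibility. Nothing supplies the units or says what MLCs are.

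**Step 5: could the PDF conversion be the cause?** For the signs this is unlikely: a less-than sign survives in item 1 of the same list, and greater-than signs with units survive in items 11 and 16. For the letters MLCs a misread cannot be excluded. It would not account for the missing units or for the direction of the signs.

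**The case against.** The strongest reply is that nobody would be misled about direction. The words say low counts, reading B fits them exactly, and item 9 may show the same habit of writing. On that view the line is only loosely drafted: the numbers 20 and 1000 are printed, the word severe indicates the scale, and no two plausible choices of unit have been shown to classify a patient differently.

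Much of this stands. The words do give the general direction, and the undefined cell type is a bigger obstacle than the missing units. What does not follow is that the line is sound. Reading B has to be supplied by the reader, against the pattern of the other laboratory limits in the list, and even then the units and cell type are absent.

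Two stronger inferences are tempting, and the documents support neither. A reader might infer that the limits are simply reversed, so that the trial admitted patients with severe cytopenia and turned away the rest. That requires reading A to be the intended and applied rule, and neither is stated. A reader might also try to rule out reading A from the screening forecast, under which about 140 are screened and "it is expected a minimum of 90 will fulfill the inclusion and none of the exclusion criteria at baseline". That forecast covers all criteria together, and the documents give no distribution of these counts, so it cannot decide the meaning of one item.

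**Conclusion.** The point holds as an internal contradiction in item 12: its words and limits disagree unless the reader assumes an entry-state parenthesis that the text does not declare. On either reading the numeric cut-off cannot be applied reproducibly, because the units are missing and MLCs is undefined, subject to the reservation about a possible misread of those letters.

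It is a limited fault that should be fixed. It affects one of 16 exclusion criteria. It changes no endpoint, analysis or stated statistical figure, and the documents give no basis for saying how many patients, if any, were misclassified. The contradiction is visible on the page. The agreement of reading B with the words rests on the two assumptions in the working: that MLCs stands for the neutrophil count, and that low means at or below the printed limit.

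**What to change.** The sponsor should reconcile the words and limits of item 12 in one amended line. That line should state:

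- the direction of each limit as an exclusion, or else mark the parenthesis explicitly as the state required for entry;
- whether one low count is enough to exclude;
- the units of each limit;
- the cell type by name, in place of MLCs.

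The sponsor confirms the cut-offs; none is proposed here. The protocol's Institutional Review Board/Ethics Committee section requires any modification to be submitted, so the amended line goes to the IRB/EC. Existing screening records are then checked against the intended rule.

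The cost is one line, one IRB/EC submission and a record check covering, on the protocol's forecast, about 140 screened patients. No new data are needed. Enrolment was projected to end on December 31, 2020. If it is complete, the amendment can no longer affect entry, but the record check and an accurate statement of the criterion in the trial report are still needed.

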## **Investigational Treatment**

### **Introduction and maintenance of everolimus**

Everolimus will be introduced at the earliest 1 month after liver transplantation for all patients to minimize the potential risks of wound healing and vascular complications of the graft. At the start of the treatment period (Day 1), patients will receive the first dose of everolimus (1 mg twice daily in 12 hr intervals)

By Day 4, the everolimus dose will be adjusted to achieve targeted C-0h blood trough level between 3-8 ng/mL. All patients will continue to receive everolimus with CNI reduced dose for 6 months. Mycophenolate will be minimized as clinically indicated in subjects (group 2) receiving everolimus and tacrolimus.

The dose of everolimus must be taken twice-daily, 12 hours apart, in the morning and evening dose AFTER tacrolimus administration (everolimus or tacrolimus dose administrations should not be more than 10 minutes apart). The morning or evening everolimus dose should be taken consistently either with or without food as the patient prefers. To prevent alteration of study drug absorption, grapefruit or grapefruit juice are not allowed throughout the study.

